Protocol: AAAF1797

Principal Investigator: [name]

Title: Randomized controlled trial of Vitamin D Repletion Regimens in Primary Hyperparathyroidism

Study Purpose and Rationale:

Vitamin D deficiency is very common in the setting of PHPT, and leads to higher PTH levels. In this study, we will investigate the impact of two different vitamin D repletion regimens over a six month period in patients with PHPT and concurrent vitamin D deficiency. We hypothesize that vitamin D repletion ameliorates the extent of hyperparathyroidism and improves biochemical, microarchitectural and biomechanical features of the disease. In addition, we will show that vitamin D can be repleted safely in patients with PHPT. This would be of great importance to the many physicians treating patients with PHPT today, who are being advised to replete vitamin D in these patients without any clear guidelines as to how best to do so.

Study Design:

40 patients with PHPT and vitamin D deficiency (25OHD less than 30 ng/ml) will be enrolled and randomized 4:1 to two different vitamin D repletion regimens. Randomization to treatment will use randomly permuted blocks. Our first group will receive 2 capsules of 10,000 IU of vitamin D once per week for the first month and then 1 capsule of 10,000 IU of vitamin D once per week for the remaining five months which should replete vitamin D deficiency and decrease PTH (our primary end-point). Control subjects (Group 2) will take 2 capsules of the placebo once per week for the first month and then 1 capsule of the placebo once per week for the remaining five months. All subjects will receive 400 IU of vitamin D each day, either in the form of a multivitamin or by itself, for the entire study. Our protocol provides 400 IU of vitamin D per day for control subjects because we felt that ethically it would not be appropriate to withhold all vitamin D from this group. A 400 IU dose is expected to raise serum 25-OHD levels minimally (2-3 ng/ml) thus allowing this cohort to serve as a valid control group ¹.

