Study drug will be dispensed at the first visit as appropriate to randomization. Participants will be instructed on and receive a printed medication administration schedule. They will be advised to begin taking their study drug immediately, and up to 500 mg of supplemental calcium but no additional vitamin D. They will be instructed about events that could be related to hypercalcemia or hypercalciuria: nephrolithiasis, nausea, vomiting, polyuria/polydipsia, or fractures.

The study will have a 6 month design, which will allow us to capture our treatment groups before and during the process of becoming vitamin D replete. Many PHPT patients are monitored without surgery for years and thus determining the safety and effect of maintaining adequate 25-OHD levels is imperative.

No vitamin D toxicity data exist in patients with PHPT. Available data in normal subjects are of limited applicability to patients with PHPT who are hypercalcemic and often hypercalciuric at the outset. However, in normal subjects hypercalcemia does not occur unless serum 25-OHD levels are above 150-200 ng/ml. The Food and Nutrition Board has set a safe tolerable upper intake level of 2000 IU daily for vitamin D3 and 2400 IU as the no-observed adverse-effect level. More recent clinical trial data suggest that these assessments are extremely conservative ². It should be noted that none of the patients

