treated by Grey et al. achieved a 25-OHD level above 50 ng/ml, and their mean increment in 25-OHD was 19 (range 6-37 ng/ml). However, because PHPT patients may be more susceptible to adverse effects due to their baseline elevations in serum and urinary calcium, the careful monitoring we propose is essential to allow conclusions about safety of repleting vitamin D in PHPT. In addition, because of this concern, we will exclude any patient with: serum calcium greater than 11.5 mg/dL; urine calcium greater than 350 mg/dL per day; active nephrolithiasis or nephrocalcinosis. We will also compare the percentage of participants who achieve a 25-OHD level above 30 ng/ml in each group, and assess the changes in serum and urinary calcium, 25-OHD and 1,25-OH₂D among groups. We will describe the time course of the normalization of 25-OHD levels in the treatment group and evaluate whether the level of vitamin D or acuity of the change in vitamin D is predictive of adverse events. We plan to analyze the data on an intent-to-treat basis, but will also do a secondary per protocol analysis based upon final vitamin D level in order to estimate achievable PTH reduction in regimen compliant subjects. Finally, we will assess patients for the development of safety outcomes. Participants whose serum calcium concentration rise above 12 mg/dL or develop nephrolithiasis (evaluation of clinical complaint) will be withdrawn. Although we will also monitor and compare the number of participants in each group whose urinary calcium level exceeds 400 mg/day, these individuals will not be withdrawn as explained in the Data and Safety Monitoring section. The frequency of patients with these outcomes at each time point will be compared among groups. We expect that the treatment regimen will be effective in achieving a vitamin D level above 30 ng/ml, while the 400 IU control group will not reach this threshold. The issues assessed here will therefore be of great value in formulating recommendations for vitamin D treatment, a key research goal of the new Consensus Guidelines, and an imperative for clinicians treating PHPT patients.

Describe how participants will be recruited:

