measure will use linear mixed models for repeated measures to assess the fixed effects of vitamin-D repletion regimen, time, regimen time interaction, random effects for intercept and standard covariates; and a covariance structure fit prior to the hypothesis test. Average time to achieve a 25-OHD level of 30 for the two vitamin-D repletion regimens will be estimated with a Cox proportional hazards model. Power and sample size calculations assume PTH is analyzed in log units, unequal sample sizes in the two groups, unequal variances in the two groups, a type I error rate of 0.05, 80% power and a two-tailed T-Test of the post-treatment PTH levels. A reduction in the treated group from 149 ± 64 ng/ml to 85 ± 48 pg/ml is larger than our original estimated effect size but consistent with the data available from our cross-sectional study for patients with 25OHD 30 ng/ml, respectively. Given the above assumptions and a desired 4:1 treatment allocation ratio, a sample size of 40 distributed 32 vs 8 meets our power goal (calculated with harmonic mean sample size of 13 per group). The analysis of safety event rates will include Fisher's Exact comparisons of between-group differences in the number of patients with hypercalcemia and/or hypercalciuria; and a Cox proportional hazards assessment of time to first AE adjusted for standard timeindependent covariates and time-dependent cumulative vitamin D dosage will be used to estimate the contribution of vitamin D to the development of the safety events. Assessments of safety events will be conducted to relate the onset of safety events to baseline vitamin-D levels, to the ramp of vitamin-D level increase and peak available vitamin-D level at time of event (to the extent known). Standard covariates for all analyses include season, weight, serum calcium and age. All power and sample size calculations based on SAS Power and Sample Size 3.1 (SAS Institute, Cary, NC).

References:

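### The average time to a 25-OHD of 30 in both arms is assigned to a Cox model, with no time summary defined and few control events expected among 8 controls

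*Combined protocol and SAP*

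**What the plan says.** The time-to-repletion analysis is one sentence in Statistical Procedures: "Average time to achieve a 25-OHD level of 30 for the two vitamin-D repletion regimens will be estimated with a Cox proportional hazards model". The section names no mean, median or restricted mean, no time horizon, and no way of getting from the fitted model to a time.

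The facts that bear on it are elsewhere in the document:

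- Entry (Study Design): "40 patients with PHPT and vitamin D deficiency (25OHD less than 30 ng/ml) will be enrolled", so everyone starts below the threshold.
- Arm sizes (Statistical Procedures): "a sample size of 40 distributed 32 vs 8 meets our power goal".
- Follow-up (Study Design): "The study will have a 6 month design".
- Expected control response (Study Design): a rise of only 2-3 ng/ml on 400 IU daily. The plan expects the treatment regimen to achieve a level above 30, "while the 400 IU control group will not reach this threshold".
- Related analyses (Study Design): "We will also compare the percentage of participants who achieve a 25-OHD level above 30 ng/ml in each group", with no test named; and "We will describe the time course of the normalization of 25-OHD levels in the treatment group", which leaves out the controls.

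The event itself is worded in two ways: a level of 30 in Statistical Procedures and a level above 30 in Study Design. Neither place says whether the first or a sustained crossing counts.

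**The concern.** The sentence promises a quantity that the named model does not directly estimate, and promises it for an arm in which the plan expects few or no events. An analyst would have to choose the summary after seeing the data. Two of the three usual choices, the unrestricted mean and the median, may not exist for controls. If no control crosses, default software output would show a very large hazard ratio with a meaningless Wald interval.

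At stake is a secondary result: how quickly the regimen repletes vitamin D and how that compares with 400 IU alone. The plan presents this kind of information as useful for treatment recommendations.

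**Working it through.** **The plan's own figure.** The document gives no number for this analysis. The figure it depends on is the allocation, and that reproduces: 40 at 4:1 is 32 and 8, and the harmonic mean is 2 × 32 × 8 / 40 = 12.8, stated as 13.

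**Assumed control crossing rate.** No baseline 25-OHD distribution is given. Suppose control baselines are spread evenly from L to 30 and all controls rise by 2 or 3 ng/ml. The fraction crossing is then rise / (30 − L):

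| L (ng/ml) | Crossing rate |
|---|---|
| 10 | 2/20 to 3/20 = 10-15% |
| 15 | 2/15 to 3/15 = 13-20% |
| 20 | 2/10 to 3/10 = 20-30% |
| 25 | 2/5 to 3/5 = 40-60% |

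**What 8 controls can support.** Let X be the number of controls crossing, X ~ Bin(8, p), with complete follow-up to 6 months. An unrestricted mean needs X = 8, a median needs X ≥ 4, and a finite hazard ratio needs X ≥ 1.

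| p | P(X=0) = (1−p)^8 | P(median not reached) = P(X≤3) | P(not all cross) = 1−p^8 |
|---|---|---|---|
| 10% | 43% | 99.5% | >99.9% |
| 20% | 17% | 94% | >99.9% |
| 30% | 6% | 81% | >99.9% |
| 40% | 1.7% | 59% | 99.9% |
| 50% | 0.4% | 36% | 99.6% |
| 60% | 0.07% | 17% | 98% |

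**Cox model with few control events.** This uses the partial likelihood with Efron ties, 32 v 8, and censoring at month 6 only. Treated crossings are assumed at months 1 to 6 as 6, 6, 6, 6, 3, 3 (30 of 32) or 4 per month (24 of 32).

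- 0/8 controls, 30/32 treated: the log-likelihood at log HR 2, 5, 10, 20 is −83.448, −81.002, −80.866, −80.865. It keeps rising, so there is no finite estimate and no upper limit. The likelihood-ratio chi-square is 28.70 (p = 8 × 10⁻⁸), with lower 95% profile limit 10.1.
- 0/8 controls, 24/32 treated: the same pattern, with chi-square 17.39 (p = 3 × 10⁻⁵) and lower limit 5.3.
- One control crossing at month 3: HR 18.1 (profile limits 3.8 to 324) with 30/32 treated, or 9.7 (2.0 to 173) with 24/32. These are finite but very imprecise.

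**Mean restricted to 6 months, same examples.**

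- Treated, 30/32: [6(1+2+3+4) + 3(5+6) + 2×6] / 32 = 105/32 = 3.28 months.
- Treated, 24/32: [4 × 21 + 8 × 6] / 32 = 132/32 = 4.13 months.
- Control, one crossing at month 3: (3 + 7×6) / 8 = 5.63 months.
- Control, 0/8: 6.0 months with standard error 0, which is just the horizon.

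**Dependence on the draw schedule.** The figures above assume monthly draws. If the same treated crossings are seen only at months 3 and 6, the results are (18×3 + 12×6 + 2×6) / 32 = 138/32 = 4.31 and (12×3 + 12×6 + 8×6) / 32 = 156/32 = 4.88 months. The first is outside the interval of 2.7 to 3.9 around 3.28.

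**Percentage above 30.** This can be estimated whatever the controls do.

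| Treated v control | Fisher p | Difference (exact 95% CI) |
|---|---|---|
| 30/32 v 0/8 | 5.9 × 10⁻⁷ | 94% (60% to 99.7%) |
| 24/32 v 0/8 | 1.7 × 10⁻⁴ | 75% (35% to 89%) |
| 24/32 v 1/8 | 0.002 | 62.5% (8.5% to 84%) |

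**The case against.** **Deriving times from a Cox fit is routine.** Arm-specific curves are a standard by-product, and times can be read from them. That is true, but the step and the summary are still unstated, and reading a time from the curve does not create a control median that the data do not reach.

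**The crossing rates may be too low.** They give every control a fixed rise and ignore fluctuation, whereas time to 30 is a first-crossing event; the plan lists season among its standard covariates. As an illustration, take a rise of 2.5 and an independent visit-to-visit SD of 3 ng/ml (both assumed). With 3 to 6 draws, the ever-crossing rate goes from 13% to 25-32% (L = 10), 17% to 34-42% (L = 15) and 25% to 50-63% (L = 20). The expectation that controls will not reach 30 may also describe the group level and not all 8 people. This stands. A reader might infer that only a restricted mean can be estimated in controls, and the documents do not support that: a median is possible if controls enter near 30 or levels fluctuate.

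**A restricted mean is no cure-all.** This stands too. At 0/8 it equals the horizon, it shifts with the draw schedule, and the withdrawal rule for high calcium or nephrolithiasis in Study Design can shorten follow-up. The fix has to deal with each of these.

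**Much is already covered.** The percentage comparison and the treated-arm time course are planned, and the treated median is very likely to be reached (over 99% if at least 70% cross). So the difficulty is confined to the control arm and the contrast. An exact test also drops the standard covariates.

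**Conclusion.** The concern holds, as a minor point. The plan assigns an average time in both arms to a model that yields a hazard ratio, and it does not define the time. For controls, an unrestricted mean is essentially never estimable (98% or more, at crossing rates up to 60%). A median is unlikely at crossing rates of 10-30% (not reached in 99.5% to 81%), and a non-finite hazard ratio has a probability of 43% to 6% at those rates. The crossing rates rest on assumed baselines and on complete follow-up; with controls close to 30, or with fluctuating levels, the control median becomes attainable and 0/8 becomes uncommon.

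Two further inferences would go too far. One is that the Cox model cannot compare the arms: even at 0/8, the likelihood-ratio test and a lower profile limit remain. The other is that the trial's main result is at risk: this is a secondary analysis, and the primary PTH ANCOVA and the sample size of 40 do not depend on it.

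**What to change.** Replace the sentence in Statistical Procedures with text that does the following:

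1. Defines the event once, as the first measured 25-OHD meeting a single stated threshold, so that Statistical Procedures and Study Design agree.
2. Reports Kaplan-Meier (or interval-censored) time-to-threshold curves by arm, with the mean time restricted to 6 months, or to the longest common follow-up if withdrawals shorten it. The text should state the 25-OHD draw schedule on which this mean depends. The median is given only where reached, and no Wald interval is given for the control mean if no control crosses.
3. Makes the between-arm contrast the percentage above 30 already planned in Study Design, with Fisher's exact test (already named for safety events) and an exact confidence interval for the difference.
4. If a Cox model is kept, uses it for a hazard ratio only, with profile-likelihood or Firth inference when control events are few or none.

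The cost is analysis wording; the same 25-OHD results are used. There are three downsides. The restricted mean depends on the horizon and visit timing and is only the horizon value at 0/8. The exact comparison is not adjusted for season, weight, serum calcium and age. Its interval is wide once a control crosses, as the 24/32 v 1/8 example shows.

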Patients with primary hyperparathyroidism will be recruited by physician referral from the population of patients seen in the Metabolic Bone Diseases Unit, Endocrine Clinic, and the Surgical Endocrine Unit. During a medical visit, eligible patients will receive information about the study and study procedures by their physician. Those patients interested in the study will give their permission to have their contact information sent to the study coordinator and PI for follow-up. Patients who do not want to hear more information about the study will not be contacted. Those patients who agree to hear more information about the study will be contacted by the PI or the study coordinator. The patient will learn more about the study, study procedures, and the consent form. Those who agree to participate will have the consent form mailed to them for further review. During their first visit, the study coordinator, or the physician, will go over the consent form and answer any other study related questions, the participant will then sign the consent form. The availability of patients from both the medical and surgical services at Columbia University Medical Center (CUMC) over the funding period should provide ample opportunity for us to enroll patients.

Statistical Procedures:

The primary statistical analysis of the 6-month endpoint will be an intent-to-treat (ITT), "as prescribed", ANCOVA assessment of between group differences in log-transformed serum PTH level adjusted for baseline serum PTH and the covariates listed below. The primary ITT analysis will be repeated with actual cumulative vitamin D intake entered as a continuous time-dependent covariate to estimate the time course of the "as treated" decrease in PTH level. Analysis of the longitudinal growth curve of each

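### Does sizing on unequal variances at 32 vs 8 oblige the primary log-PTH ANCOVA to name an unequal-variance estimator?

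*Combined protocol and SAP*

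**What the plan says.** All the relevant text is in the Statistical Procedures section of the combined protocol and SAP, apart from two remarks under Study Design.

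- Primary analysis: an intent-to-treat "ANCOVA assessment of between group differences in log-transformed serum PTH level adjusted for baseline serum PTH and the covariates listed below". The covariates are given later: "Standard covariates for all analyses include season, weight, serum calcium and age". No residual variance model, robust standard error or degrees-of-freedom method is stated. The only wording on covariance structure belongs to the longitudinal mixed models.
- Sizing: on log PTH, with "unequal sample sizes in the two groups, unequal variances in the two groups, a type I error rate of 0.05, 80% power". The effect is "A reduction in the treated group from 149 ± 64 ng/ml to 85 ± 48 pg/ml", the comparison behind the calculation is "a two-tailed T-Test of the post-treatment PTH levels", and the result is that "a sample size of 40 distributed 32 vs 8 meets our power goal".
- Study Design: "Randomization to treatment will use randomly permuted blocks". It also announces a "secondary per protocol analysis based upon final vitamin D level in order to estimate achievable PTH reduction in regimen compliant subjects".

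**The concern.** The plan expects unequal variances when it counts patients and is silent about them when it analyses those patients. Pooling is fairly harmless with equal arms but not at 4:1, where the larger arm supplies most of the variance estimate while the smaller arm drives most of the true uncertainty. If the larger arm is the more variable, the pooled interval is too wide; if the smaller arm is, the interval is too narrow. With 8 controls, the interval for the PTH effect therefore depends on an estimator that the plan does not name, and that could in principle be chosen after the residuals have been seen.

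**Working it through.** **Inputs from the Statistical Procedures section.** 149 ± 64 and 85 ± 48; 32 treated and 8 controls; log scale; two-sided 0.05; 80% power. The ng/ml against pg/ml mismatch in the effect sentence is a unit slip and does not affect what follows.

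**Assumptions not in the documents.** PTH is lognormal, ± means SD, controls stay at 149 ± 64, all 40 are analysed, and pooling is the default reading of ANCOVA.

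**1. Log-scale SDs**, from sqrt(ln(1 + CV²)):
- Control: CV = 64/149 = 0.430; variance ln(1 + 0.430²) = 0.169; SD 0.411.
- Treated: CV = 48/85 = 0.565; variance ln(1 + 0.565²) = 0.277; SD 0.526.
- Difference: ln(149/85) = 0.561.

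**2. The plan's sample size.** The unequal-variance standard error is sqrt(0.169/8 + 0.277/32) = 0.173, with about 13.4 Satterthwaite df. The noncentrality is 0.561/0.173 = 3.25, which gives 85% power. The smallest 4:1 design reaching 80% is 8 + 32 = 40. The harmonic mean is 2/(1/32 + 1/8) = 12.8, which the plan rounds to 13. Both figures reproduce.

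**3. Effect of pooling, no covariates.**
- Pooled variance: (7 × 0.169 + 31 × 0.277)/38 = 0.257.
- Pooled standard error: sqrt(0.257 × (1/8 + 1/32)) = 0.200, or 1.16 times the true 0.173.
- Simulated coverage of a nominal 95% interval: 97.6% pooled, 94.8% Welch.

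**4. Effect of pooling in the ANCOVA.** Intercept, arm, baseline PTH, weight, calcium, age and three season terms make 9 parameters, leaving 40 − 9 = 31 df.
- Pooled coverage is 97.0 to 97.3% if the covariates explain nothing, and 97.5 to 98.2% with a common baseline slope at correlation 0.5 to 0.7.
- HC2 standard errors with Bell-McCaffrey df cover about 96%. Arm-specific variances with Kenward-Roger cover 94.6%.

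**5. Why the interval barely moves.** In the ANCOVA the pooled standard error is about 12% too large, but it takes a critical value of 2.04 (31 df). HC2 takes 2.21 (10.8 df). The multipliers on the true standard error are 1.12 × 2.04 = 2.28 and 2.21, so HC2 is about 3% narrower on the log scale. For a true ratio of 85/149 = 0.57, with both residual SDs reduced by sqrt(0.75) to represent a baseline correlation of 0.5, typical intervals are:

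| Estimator | Interval for the ratio | Power |
|---|---|---|
| Pooled | 0.39 to 0.84 | 84% |
| HC2, Bell-McCaffrey | 0.39 to 0.83 | 84% |
| Arm-specific, Kenward-Roger | 0.40 to 0.82 | 84% |

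If the total SDs are kept at 0.41 and 0.53 with a common slope at correlation 0.5, power is 79% pooled and 81% HC2. With no baseline correlation it is 71% pooled, 72% HC2 and 73% Kenward-Roger. The gain from leaving pooling is 0 to 2 points throughout.

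**6. The opposite case: equal variances (0.50 each).** Power falls from 82% pooled to 77% with HC2 and 75% with Kenward-Roger at correlation 0.5, and from 70% to 65% and 63% at correlation 0. The loss is 82 − 77 = 5 to 82 − 75 = 7 points in the first case and 70 − 65 = 5 to 70 − 63 = 7 in the second.

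**7. Type I error.** With no treatment effect at all, randomisation gives both arms the same distribution of log PTH. The variances are then equal and the pooled test holds 5%. A level of about 3% arises only if treatment changes the spread of log PTH while leaving its mean unchanged, which the plan nowhere anticipates.

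**The case for a change.** The best case for a change is that the interval is the useful output of this trial and that, on the plan's own variance assumption, a pooled 95% interval is not a 95% interval. Naming the estimator would cost one sentence, leave the sample size alone and remove a choice that could otherwise follow unblinding. The direction is not guaranteed either: with the two log SDs swapped, the pooled test would run at about 8%.

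Part of this stands. The plan is silent, the over-coverage is real under the stated assumptions, and naming the estimator in advance is good practice. The rest is weaker. No figure in the documents makes the control arm the more variable on the log scale. The raw SDs do point that way, and used as they stand would give about 90% coverage, but the plan analyses log PTH. The stated aim of estimating an achievable reduction belongs to the secondary per-protocol analysis, not to the intent-to-treat ANCOVA. The first-choice remedy, HC2 with Bell-McCaffrey df, removes only about half of the excess coverage. And if the variances are close to equal, either remedy takes power at correlation 0.5 from 82% to below the 80% goal.

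**Conclusion.** No change is needed. The plan does not say that it pools, so it contains no contradiction, only an unstated detail. Either reading leads to practically the same interval and the same conclusion: coverage of about 97 to 98% if pooled, an upper limit for the ratio of 0.84 against 0.83, and 0 to 2 points of ANCOVA power. The error is conservative, and the test is valid when treatment has no effect. Choosing between estimators is a fair trade-off: 0 to 2 points gained if the variances differ as assumed, 5 to 7 lost if they do not.

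This rests on lognormal PTH, controls remaining at 149 ± 64, and assumed baseline correlations, because the plan gives no log-scale SD, no separate control-arm SD and no residual variance after covariates. An analyst may reasonably fit either model as primary and show the other as a sensitivity analysis.

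### The protocol says it will show that repletion is safe, but the safety event comparisons it describes are difference tests on 32 versus 8 patients, which cannot support that claim

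*Combined protocol and SAP*

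**What the plan says.** Study Purpose and Rationale states, after the efficacy hypothesis: "In addition, we will show that vitamin D can be repleted safely in patients with PHPT". Study Design takes this further. Because these patients may be more vulnerable, "the careful monitoring we propose is essential to allow conclusions about safety of repleting vitamin D in PHPT", and "The issues assessed here will therefore be of great value in formulating recommendations for vitamin D treatment".

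The safety outcomes are named in Study Design. "Participants whose serum calcium concentration rise above 12 mg/dL or develop nephrolithiasis" are to be withdrawn. The investigators will also compare "the number of participants in each group whose urinary calcium level exceeds 400 mg/day, these individuals will not be withdrawn". The planned comparison of these outcomes reads: "The frequency of patients with these outcomes at each time point will be compared among groups".

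Statistical Procedures lists, for safety event rates, Fisher's "Exact comparisons of between-group differences in the number of patients with hypercalcemia and/or hypercalciuria" and a Cox model of time to first adverse event. The Cox model includes cumulative vitamin D dose as a time-dependent covariate and "will be used to estimate the contribution of vitamin D to the development of the safety events". Further assessments relate the onset of events to vitamin D levels. The section gives no calcium thresholds for its terms hypercalcemia and hypercalciuria. The sample size, 32 versus 8, is justified by PTH alone.

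**The concern.** A statement that the trial will show safety needs an analysis that can rule out an unacceptable event rate. Fisher's test and the time-point comparisons ask a different question, namely whether the arms differ. Failing to find a difference is not evidence that the rate is low, least of all with 8 controls. The text sets no margin, no acceptable rate and no interval, and does not say how a non-significant result will be read.

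The results are meant to inform treatment recommendations. If 6/32 treated patients and 0/8 controls had an event, the test would be clearly non-significant although the data would be compatible with a large excess. Without prespecified intervals, nothing in the written analysis would put that uncertainty in front of the reader.

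**Working it through.** **Inputs.** From Statistical Procedures: 32 treated and 8 controls; type I error 0.05, two-tailed and 80% power (both stated for PTH); PTH 149 (SD 64) and 85 (SD 48). From Study Design: six months of follow-up. The documents give no safety event rates, so all rates below are assumptions shown over a range.

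**The plan's own figure (PTH).** The harmonic mean of 32 and 8 is 2×32×8/40 = 12.8, which rounds to the stated 13. On the raw scale the difference is 149 − 85 = 64, and the root-mean-square SD is √[(64² + 48²)/2] = √3200 = 56.6. The normal formula gives 2×(1.960 + 0.842)²×3200/64² = 12.3, so 13 per group at 1:1. At 4:1 it gives (1 + 1/4)×(1.960 + 0.842)²×3200/64² = 7.7, so 8 controls and 40 in total. The size therefore reproduces, and it comes from PTH only.

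**Fisher's test at 32 versus 8, no control events.** With m events in all, the number falling among the 8 controls is hypergeometric (40 patients, 8 controls, m events). The two-sided p-value sums every outcome no more probable than the one observed.

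- m = 12: P(0 in controls) = 0.0404. Adding the less likely outcomes in the other tail (5 or more control events, 0.0386) gives p = 0.079.
- m = 13: P(0 in controls) = 0.0289. Adding 6 or more control events (0.0085) gives p = 0.037.
- m = 6: p = 0.32.

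So 13/32 (41%) is the smallest significant count against 0/8. Against 1/8 it is 18/32 (p = 0.046; 17/32 gives 0.054).

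**Power.** Power is the sum, over all significant tables, of Binomial(32, treated rate) × Binomial(8, control rate). When the control rate is 0%, this is simply P(at least 13 of 32).

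| Assumed true treated rate | Control 0% | Control 5% |
|---|---|---|
| 20% | 0.6% | 0.4% |
| 30% | 13% | 9% |
| 40% | 54% | 37% |
| 50% | 89% | 68% |

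Power of 80% needs a true treated rate of about 46.5% against 0%.

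**What the data could bound.** With no events in n patients, the exact upper limit is 1 − α^(1/n), where α is the one-sided tail.

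- 0/32, two-sided 95%: 1 − 0.025^(1/32) = 10.9%.
- 0/32, one-sided 95%: 1 − 0.05^(1/32) = 8.9%.
- 0/8, two-sided 95%: 1 − 0.025^(1/8) = 36.9%.
- 1/32, two-sided 95% (Clopper-Pearson): upper limit 16.2%.
- 6/32, two-sided 95% (Clopper-Pearson): 7.2% to 36.4%.

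For the risk difference against 0/8, the exact unconditional upper limit (score statistic, one-sided 2.5%) is 12.1 points for 0/32, 18.8 for 1/32 and 37.6 for 6/32.

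**Early leavers.** One control counted as an event adds 1/8 = 12.5 points to the control rate. One treated patient adds 1/32 = 3.1 points to the treated rate.

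**The case against.** PTH is the primary endpoint and safety is an additional aim. Low power for a safety comparison is usual in a 40-patient trial, and nobody would enlarge this one for that reason. The plan also goes beyond testing: the Cox model estimates a dose contribution, changes in serum and urinary calcium are compared, and Fisher's test already works on patient counts. The list of safety analyses is introduced as what will be included, which is not exhaustive. Study Design refers to a Data and Safety Monitoring section that is not part of the text available. No interval is mentioned for any endpoint, PTH included, so silence may only reflect a short statistics section.

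Most of this stands, and it limits the point. A reader might infer that the investigators intend to treat a non-significant test as proof of safety; the text does not say so. A reader might also infer that the trial has no safety criterion anywhere; that cannot be said without the missing section. Study Design cites that section only for why patients with high urinary calcium stay on study.

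The objection does not remove the mismatch. The Cox estimate is a relative dose association and the calcium analyses describe mean change; neither limits the share of patients with an event. The serum and urinary calcium thresholds are a withdrawal rule and an event definition for individual patients, not a rate at which the regimen would be judged safe.

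**Conclusion.** The concern holds in a limited form. In the text available, the event-rate comparisons cannot deliver the stated conclusion that repletion is safe. Against 0/8 controls, up to 12/32 treated events would be non-significant, and power is 13% even at an assumed 30% versus 0%. These p-values and limits follow exactly from 32 versus 8 with complete follow-up; the power figures rest on assumed rates.

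Two stronger readings are not supported. The first is that 32 treated patients can never exclude a rate below 10.9%. That figure belongs to a two-sided 95% interval; at one-sided 95% it is 8.9%, and the documents set no level for safety. The second is that the trial must be larger: modest, honest estimation is possible at the planned size. The PTH analysis is unaffected. The change should be made, but it is one of wording and reporting.

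**What to change.** 1. In Study Purpose and Rationale, replace the promise to show safety with an aim to estimate the rate of safety events.
2. Make the main safety summary the cumulative number of randomised patients per arm, by month 6, with each Study Design outcome: serum calcium above 12 mg/dL, urinary calcium above 400 mg/day, and nephrolithiasis. Include events that lead to withdrawal, because frequencies at later visits lose those patients. Give exact two-sided 95% intervals per arm and for the risk difference. Keep Fisher's test as descriptive, and the Cox and calcium-change analyses as supportive. Using these outcomes for the undefined terms in Statistical Procedures is an assumption that the investigators should confirm.
3. State in advance that, with complete follow-up, 0/32 events gives an upper limit of 10.9% (two-sided 95%; 8.9% one-sided 95%) and 1/32 gives 16.2% (two-sided 95%). If a claim of safety is kept, prespecify the highest acceptable event rate and the confidence level.
4. For each outcome, report per arm how many patients left early without the event. If a worst case is shown for the risk difference, count early leavers as events in the treated arm only and as event-free in the control arm; counting control leavers as events would shrink the apparent excess.

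The cost is wording in the protocol and analysis plan, with no extra patients or data. The safety claim becomes less favourable, and the intervals will be wide, above all for the 8 controls (upper limit 36.9% even with no events).
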